b. Sharing of Results with Subjects

The results generated in this study are experimental in nature and will not be shared with study subjects.

c. Data and Specimen Banking

Laboratory Evaluations: Not applicable. This study does not propose to collect or store human specimens.

Data will be de-identified with a unique subject ID that on the PI and RA will be able to link the ID to the person. Subject information and study data will be stored behind a locked office in a locked cabinet at OHSU (if paper) or behind a secure Oregon Health & Science University (OHSU) firewall on network drives requiring password authentication (if electronic). If being stored at the VA, it will be kept on the secure VAPORHCS network folder ([name]) or in locked cabinets in locked office P5F-153 bldg 104 (if paper). Data will be stored at OHSU in our secure database and may be used for future research. We will also ask permission from our subjects to be maintain their data in our Balance Disorders Laboratory repository (eIRB# 7797).

As required by the DOD, we will upload de-identified data to Federal Interagency Traumatic Brain Injury Research Informatics System (FITBIR) quarterly. The data will have no PHI uploaded and only quantitative data will be uploaded.

8. Data Analysis

Analysis of oculomotor data: We will use eye tracking along with inertial sensors on the head and trunk to examine how well the subjects is able to maintain a stable gaze, particularly in the horizontal and vertical VOR conditions, by examining average eye velocity throughout the condition. Secondary measures will be the cross-covariance between eye velocity and head angular velocity.

Analysis of postural sway data: Postural sway will be automatically quantified in the ML direction using APDM software during each stance condition by calculating the RMS around the mean acceleration (acc), a metric representing sway dispersion (APDM 2013). Our primary measure for this test will be the averaged ML RMS during the Instrumented Modified BESS using an inertial sensor to measure linear acceleration of the body since

[figure not shown]
this test could classify mTBI best in our previous study ([name] et al., under review). Other temporal and spatial metrics such as sway velocity, frequency and jerkiness will be simultaneously collected for secondary analysis. Analysis of head stability during gait: Our primary measure during gait will be the lumbar to head attenuation of acceleration quantified by the attenuation coefficient (Iosa, Mazzà et al. 2010). The attenuation coefficient quantifies the amount of acceleration that is dissipated when moving from inferior to superior body segments. It is calculated using the ratio of head RMS acceleration to lumbar RMS acceleration, with a larger attenuation coefficient indicating more acceleration was dissipated from the lumbar to the head. Wireless eye tracking goggles during each trial will be analyzed to obtain secondary measures including the cross-correlation and time lag between eye, head, and trunk rotational velocities. The eye tracking glasses and head sensor will be used to quantify change in visual field and the quality (amplitude, symmetry, smoothness of head movement) of purposeful head turning, respectively, when participants are asked to walk while performing head turns.

Analysis of complex turning: Head, sternum, and lumbar mounted inertial sensors will quantify the angular velocity of reorienting segments, specifically of the head, trunk, and pelvis. The primary outcome will be the peak axial angular velocities head for each turn. Mobile eye tracking glasses will quantify the reorientation velocity and timing of the eyes with respect to the head. Eye-to-head, head-to-trunk, and head-to-lumbar sequential timing, along with peak axial angular velocities of the trunk and pelvis, will be calculated from the inertial sensors as secondary outcomes.

Analysis of CSMI data: The primary outcome measures are the parameters derived from a model-based interpretation of CoM sway evoked by pseudorandom stimuli (Table 4). The procedure for calculating these parameters is to (1) calculate CoM angular displacement from experimental measures of hip and shoulder displacement on each test trial, (2) use Fourier methods to calculate a frequency response function, FRF (Pintelon and Schoukens 2001), and (3) adjust parameters of a model of the balance control system using a constrained optimization algorithm until the model-derived FRF optimally matches the experimental FRF (Peterka 2002, Peterka 2003).

Sample size calculation for Aims I and II:

Sample size estimation for the efficacy of early versus later physical therapy intervention on patient-reported outcomes (Aim I) was derived from a published study evaluating the effects of early initiation of balance exercises after acute, peripheral vestibular balance disorders as measured by the Dizziness Handicap Inventory (DHI) (Jacobson and Newman 1990, Bamiou, Davies et al. 2000). Patients who presented for treatment within six months of the onset of vertigo had lower DHI scores following physical therapy compared to those who waited longer (22 versus 51, Mann-Whitney, $p=0.007$, Cohen's $d=0.432$). This significant difference in symptomatic outcome based on the effect of physical therapy latency is expected to be at least as profound in the proposed cohort given this study investigates the effects of an even earlier initiation of physical therapy, than the six or more-month latency of the described study. Assuming the effect size between early and late therapy initiation observed in the literature is equivalent in magnitude to the effect size expected in the proposed cohort, a significant effect of time would still be observed at $\alpha=0.05$ with 80% power with a sample size of 36 per group, for both the wearable sensor group and standard physical therapy regimens.

Study design for Aims I and II

We demonstrated the resolution of symptoms in very mild mTBI was associated with increased head rotation during walking with head turns (Fig. 6). Power analysis for the secondary outcome (head-turn velocity) was derived from our pilot data assessing improved head velocity over time. In an mTBI cohort, a significant rate of change was observed with increasing head-turn velocity over time ($N=26$, $t=4.07$, $p<0.001$, Cohen's $d=0.798$, Fig. 6). With the same sample size of 36 per group, a significant effect of early versus later intervention would still be observable at $\alpha=0.05$ with 80% power, if there is at least a 56% difference in the effect size ($d=0.446$) between the two time-course arms for either intervention group. Similarly, this effect size could also be observed to be statistically significant between the feedback-enhanced intervention and standard exercise regime within either the time to rehabilitation cohorts. Assuming a dropout rate of ~20% over the study period, the expected effects sizes would be found to be significant with a final recruitment of 40 subjects for each of the four groups; totaling 160 people with mTBI for aims I and II combined.

II combined.

Primary outcome: DHI The final sample for Aims I and II will consist of four distinct groups: A) early rehabilitation using wearable sensors at-home, B) early intervention with traditional at home exercise program, C) late rehabilitation using wearable sensors at-home, and D) late intervention with traditional at home exercise program. Linear mixed-effects models will be used in an intention-to-treat design to assess the continuous rate of change in DHI over time in each group. Mixed-effects models will be used to account for within-subject correlation in the repeated measurements across time while addressing any missing data due to dropouts or absentee visits. An on-treatment comparison will also be leveraged, using ordinary least squares to model to bulk change in study outcomes from baseline to study exit for all subjects completing the study.

To compare the effect of early versus late intervention, the main effect of time (Aim I, comparing groups AB to CD) will be assessed in the mixed-effects model. To compare the effect of rehabilitation with home monitoring versus standard-of-care rehabilitation, the main effect of treatment will be assessed in the mixed-effects model (Aim II, comparing groups AC to BD). To compare whether the effect of at-home monitoring is different between early and late rehabilitation, the interaction between time and treatment will be evaluated using the mixed-effects model. Beyond the main effects of time, treatment and their interaction, individual contrasts among groups will be considered using an ANOVA framework to compliment mixed-effects regression model.

Mixed-effects models will also incorporate covariates found to influence study outcomes, including, but not limited to, age, gender, vestibular function. For the intention-to-treat mixed-effects models, an unstructured error covariance structure will be utilized and parameters will be estimated using restricted maximum likelihood procedures. Missing data points in the analytical sample are considered missing at random and the above approach is sufficient under this assumption. Results will be considered significant at $\alpha=0.05$ with Holm-Bonferroni adjustments to correct for multiple comparisons among the various outcome measures. Model fit and integrity will be examined using a combination of formal fit criteria and visual inspection of residual plots.

Secondary Outcome measures will be assessed using the mixed-effects models as described above to determine the effect of time and treatment on each outcome. To determine the meaningful change of head stability metrics after rehabilitation, the minimal detectable change of our novel outcome measures presented in Table 2 such as attenuation coefficient, cross-covariance of eye, head, and lumbar movements, peak axial rotational velocities, and sequential timing of reorientation will be calculated. Minimally clinically important difference for these novel measures will also be calculated using an anchor-based approach where clinically meaningful difference is based on PGIC.

9. Privacy, Confidentiality, and Data Security

Identifiers: Subjects will be assigned a coded study identification (ID) number generated after written informed consent has been obtained. The subjects' name and unique ID number will be recorded in an electronic file, stored on a password-protected secure drive. Research records will be stored in a confidential manner so as to protect the confidentiality of subject information. Data collection forms will be labeled using unique study ID numbers and will not have personal identifiers.

Confidentiality: To ensure and protect the privacy of the study subjects and to maintain confidentiality of the data, the following activities for data and safety monitoring will be in place for the study: 1) A detailed plan will be approved by the Institutional Review Board (IRB) before recruitment begins, 2) Data will be coded upon collection with the key to the code held separately from the data and accessible only to IRB approved study personnel who need to know. Subject information and study data will be stored behind a locked office in a locked cabinet at OHSU (if paper) or behind a secure Oregon Health & Science University (OHSU) firewall on network drives requiring password authentication (if electronic). If being stored at the VA, it will be kept on the secure VAPORHCS network folder ([name]) or in locked cabinets in locked office P5F-153 bldg 104 (if paper). The representatives of the US Army Medical Research and Material Command (USAMRMC) are eligible to review study records. The persons who are authorized to use and disclose the data from this study are the approved investigators, other research professionals at OHSU who are participating in the conduct of this research protocol, and the OHSU/Veteran Affairs (VA) IRB. All data will be safeguarded in accordance with Health Insurance Portability and Accountability Act (HIPAA). The knowledge of any pending compliance inspection/visit by the USAMRMC, or other government agency concerning clinical investigation or research, the issuance of Inspection Reports, warning letters, or actions taken by any Regulatory Agencies, including legal or medical actions, and any instances of serious or continuing noncompliance with the regulations or requirements will be reported immediately to OHSU and/or the Portland VA Human Research Protection Office, and to the Department of Defense and/or USAMRMC. Representatives from USAMRMC are eligible to review study records upon request. Data collected in this study do not include any sensitive information, such as history of communicable diseases that are required to be reported to state or local authorities.

Data capture, verification and disposition: Data will be gathered from questionnaires and instrumented assessments, and entered into the web-based Research Electronic Data Capture system (REDCap) and into the OHSU Balance Disorders database. REDCap is a secure electronic database administered by OHSU. Hard copies of these records will be stored behind a locked office in a locked cabinet at OHSU or if at the VA on the secure VAPORHCS network folder ([name]) or in locked cabinets in locked office P5F-153 bldg 104 (if paper). The de-identified Mobility Lab data will be collected on a password-protected and data-encrypted laptop computer and

uploaded after each test session to an OHSU secure server, where the Balance Disorders database is located. The computer that will store the project database will be protected by current network security behind OHSU firewall. An institutional computer account and password will be required to access the computer storing the recruitment database and the images. In addition, the REDCap database is password protected, and only project personnel approved by [name] will be given access. Any hard-copy research records and consent forms will be stored in a locked file cabinet within a locked, secure office. Hard-copy and electronic research records will be kept for seven years, in compliance with HIPAA, or one year after publication, whichever is longer. VA record will be kept indefinitely or as directed by the VA standards. All identifiers will be removed at the completion of the study and it will not be possible to link the data to individuals after that time.

Adaptation during COVID- 19 restrictions: All data collected over the phone or through virtual visit will be recorded on REDCap and stored on a secure OHSU server, which only study team members have access to. The study team member and participant will do all remote virtual visits over a secure Wi-Fi network.

10. Provisions to Monitor the Data to Ensure the Safety of Subjects

See the [Data and Safety Monitoring Plan](#) form for details.

11. Risks and Benefits

a. Risks to Subjects

Information that identifies participants will be used in this study and shared with research staff and non-VA researchers. A breach in confidentiality and a resulting loss of privacy could result in monetary loss due to identity theft. However, the research team will make every effort to protect private health information and guard against any loss of privacy.

Musculoskeletal injury - There is a low risk of joint, tendon, or muscle pain, inflammation, or swelling during or after a testing session of gait and balance. The risk is reduced by use of well-trained assistants and also by the mild nature of the gait, balance and vestibular testing.

Exacerbation of symptoms - There is a low risk that existing symptoms such as dizziness will become worse by performing the tests and performing rehabilitation.

Emotional Distress - Some of the questions asked may be personal or embarrassing. People may refuse to answer them if they don't want to. Also, they may learn information about their balance and walking and that could be upsetting to them.

Falls - The balance and walking tasks may cause them to lose their balance or fall. However, our trained research assistants will walk alongside them at all times for safety. All safety measures will be taken to ensure a secure and comfortable environment. People will be allowed to take a break from the balance and walking tasks whenever necessary. For balance testing on the force plate, people will be secured in a harness for safety.

Nausea - There is a risk during some of the vestibular testing that some people will experience nausea and or dizziness, in which case we stop the test immediately.

Wearable sensor system - The wearable sensors worn on the body are commonly used in other laboratory studies assessing balance and gait. There is no identifiable information stored on these sensors. These sensors are non-invasive and may cause minimal discomfort, no greater than wearing a headband, wristwatch or belt.

Biofeedback sensor system- These sensors used for biofeedback are the same as the sensors in the wearable sensor system. There is no identifiable information stored on these sensors. These sensors are non-invasive and may cause minimal discomfort, no greater than wearing a headband, wristwatch or belt.

Other Risks: There is a small risk that people may experience some ear discomfort when having your ears examined and with wearing earphones during testing. Possible temporary discomfort may be experienced during preparation and placement of the electrodes on their skin. This is rare and lasts only a short period of time. Some tests require wearing video goggles over the eyes, these may also cause discomfort. All sounds will be presented at levels where there is minimal risk of damage or discomfort. The vestibular-evoked potential tests involve the presentation of brief but loud sounds, if they find the sounds too loud we will stop the tests.

b. Potential Benefits to Subjects

Subjects and physical therapist will be compensated for their participation in this study. Subjects who participate in Aim I and Aim II will receive free physical therapy. Subjects may or may not personally benefit from being in this study. However, by serving as a subject, they may help us learn how to benefit patients in the future. All rehabilitation will be provided free of charge.

Short-term impact: Anticipated outcomes in the short term are to facilitate evidence-based recommendation for timing of physical therapy intervention for mTBI, particularly for those with complaints of imbalance. Based on results from this project and the expected benefits of early physical therapy, we expect patients with mTBI will have faster and more consistent referrals to physical therapy, thereby facilitating faster recovery. We expect the short-term impact will be immediately addressed within OHSU clinics who see patients with mTBI. Another short term impact will be mTBI-specific protocols implemented into the commercially available APDM Mobility Lab system. These test protocols will be readily available for researchers and clinicians.

Long-term impact: Our long term goals for this project are to produce more evidence-based rehabilitation and to ultimately improve care after mTBI. We believe that implementation of the findings from this research can be readily adopted into military protocols for post-mTBI care and have the potential to produce more long-term efficacious balance rehabilitation. An important long term impact of this work could clarify best practices for the rehabilitation of balance deficits by providing evidence regarding when to initiate rehabilitation and by producing protocols for utilizing wearable sensors in assessing and treating balance deficits after mTBI. We expect the use of wearable, inertial sensors will progressively increase throughout clinical, field-side or in-theatre environments as technology becomes less expensive and more widely accepted. This project will result in a portable, wireless, and easy-to-use product for physical therapists to use when training complex balance and vestibular rehabilitation exercises. The use of wearable sensors, as proposed in our project, is gaining momentum in the civilian and military populations as a method to detect mTBI. Yet, the use of inertial sensors in rehabilitation settings for clinical care is still lacking. This project will produce a system with wearable sensors to augment rehabilitation by providing feedback on the quality of head and trunk movements that are difficult to quantify visually. We anticipate that implementing this system will significantly improve the efficacy of rehabilitation following mTBI, reduce the chronic effects of mTBI and improve quality of life after mTBI. More effective rehabilitation will also lower the economic burden of mTBI on health care costs.

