Aim I. Early Intervention: To determine the effects of early versus late rehabilitation for balance deficits in mTBI. We hypothesize that early rehabilitation initiated at the initial physician visit will improve outcomes more than standard of care (later initiation of physical therapy) in people with mTBI who have complaints of imbalance. We will also determine clinically meaningful change measures due to rehabilitation for objective measures of head stability during gait, based on Patient Global Impression of Change Scale (Hurst and Bolton 2004). We will randomize 160 people with mTBI, between the ages of 18 and 60, into early rehabilitation (within first 2 weeks after physician visit) or late rehabilitation (standard of care; ~60 days from first physician visit). People will be tested before and after a 6-week rehabilitation program and again 6 months later to determine long-term effects. Our primary outcome to measure efficacy of rehabilitation is the Dizziness Handicap Inventory (DHI). Secondary outcomes will be structured along the International Classification of Function and Disability (ICF) models framework. We will measure baseline peripheral vestibular and ocular motor function and other covariates in rehabilitation efficacy. In Aim I, we will 1) determine the role of timing in rehabilitation after mTBI and 2) determine meaningful change measures of novel head stability and gait metrics after rehabilitation.

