The proposed interventional study (Aims I and II) will involve 160 human participants for intervention, all of whom who have sustained a mild traumatic brain injury (mTBI) and have complex, multisensory system impairment and complaints of imbalance and 10 subjects for validation. Aim III will involve a total of 80 human participants: 25 subjects who have sustained an mTBI with balance and/or vestibular deficits and 50 healthy control subjects and 5 physical therapists. The Oregon Health & Science University (OHSU) Concussion Management Clinic currently sees 1,200 new concussion patients per year and the primary care clinics at OHSU see approximately 3,000 mTBI patients per year.

a. Number of Subjects

The proposed interventional study (Aims I and II) will involve 160 human participants for intervention, all of whom who have sustained a mild traumatic brain injury (mTBI) and have complex, multisensory system impairment and complaints of imbalance and 10 mTBI subjects for validation. Aim III will involve a total of 80 human participants: 25 subjects who have sustained an mTBI with balance and/or vestibular deficits and 50 healthy control subjects and 5 physical therapists. A subset of (approx. 100) healthy adults will be tested to validate and provide normative data with the updated testing protocol.

b. Inclusion and Exclusion Criteria

Inclusion criteria for Aims I and II: Participants may be either Veterans or non-Veterans and must: 1) have a diagnosis of mTBI based upon VA/DoD criteria (Control and Prevention 2014, Defense 2015), 2) be between 18-60 years-old, 3) be within the acute or post-acute stage (< 12 weeks post-concussion) according to the VA/DoD clinical practice guidelines (Group 2016), 4) be able and willing to come to OHSU for physical therapy and perform home exercise program daily for 6 weeks, 5) have no or minimal cognitive impairment; a score between 0 and 9 on the Short Blessed test, and 6) have a SCAT sub score of 1 or higher on balance, dizziness, nausea, headache, or vision AND a minimum total score of 15.

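### The planning effect d=0.432 does not give 80% power with 36 per group, and it comes from a six-month contrast inside whose early category both trial arms fall

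*Protocol*

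**What the plan says.** Protocol section 8, under the sample size for Aims I and II, derives the Aim I calculation from a study of early balance exercise in acute peripheral vestibular disorders. "Patients who presented for treatment within six months of the onset of vertigo" are reported to have done better: they "had lower DHI scores following physical therapy compared to those who waited longer (22 versus 51, Mann-Whitney", with p=0.007 and a Cohen's d of 0.432. The benefit of earlier therapy "is expected to be at least as profound in the proposed cohort", on the ground that therapy here starts even sooner. The literature effect is then assumed equal to the trial effect, and 80% power at alpha 0.05 is claimed with 36 per group, for the sensor regimen and for the standard regimen.

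The text that follows repeats 36 per group for head-turn velocity (d=0.446), assumes about 20% dropout, and sets recruitment at 40 in each of four groups, 160 in all. The Aim I test pools the two home-exercise regimens: groups A and B (early) against C and D (late).

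On timing, section 5b requires participants to "be within the acute or post-acute stage (< 12 weeks post-concussion". Section 2 (Aim I) places late therapy at about "60 days from first physician visit". Section 6 (Intervention) gives approximate starts of 2 and 8 weeks after the physician appointment.

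The SAP tests a group by time-since-injury interaction in a mixed model and contains no power calculation.

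**The concern.** Two things look wrong. The stated sample size does not appear to follow from the stated effect: 36 per group is small for a between-group d near 0.43. And the effect comes from patients treated before versus after six months, whereas this trial compares two starts a few weeks apart, both soon after injury.

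If both points hold, the Protocol claims 80% power that the design does not deliver on its own input, and the input is not evidence about the contrast under test. Anyone judging a non-significant DHI result against the stated plan would credit the trial with more sensitivity than it had.

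**Working it through.** **Inputs (Protocol).** d=0.432, alpha 0.05, power 80%, 36 per group, DHI 22 versus 51 and p=0.007 (section 8, sample size); about 20% dropout and 40 per group (section 8, following text); 1:1 allocation to timing (section 6); entry under 12 weeks after injury (section 5b); late start about 60 days after the visit (section 2). Sidedness is not stated; two-sided is assumed here.

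**1. The stated 36 per group.**

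n per group = 2(z₀.₉₇₅ + z₀.₈₀)² / d² = 2(1.960 + 0.842)² / 0.432² = 15.70 / 0.1866 = 84.1, so 85. The t-based solution is 85.1, so 86. The Protocol's 36 is not reproduced.

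Power at 36 v 36: Φ(0.432 × √18 − 1.96) = Φ(−0.127) = 45%; t-based, 44%. One-sided testing does not recover it: 67 per group are needed and power at 36 v 36 is 57%.

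**2. The contrast that will be tested.** Two regimens pool to 2 × 36 = 72 evaluable, or 2 × 40 = 80 randomised, per timing arm. Taking off the stated 20% leaves 80 × 0.8 = 64. (Per group, 40 × 0.8 = 32, not 36; keeping 36 would need 36 / 0.8 = 45.) Two-sided t-based results:

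| Comparison | n per side | Power at d=0.432 | Smallest d with 80% power |
|---|---|---|---|
| Early v late within a regimen | 36 | 44% | 0.67 |
| AB v CD, after 20% dropout | 64 | 68% | 0.50 |
| AB v CD, 2 × 36 | 72 | 73% | 0.47 |
| AB v CD, no dropout | 80 | 78% | 0.45 |

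With 72 per arm, power is 43% at d=0.3 and 22% at d=0.2.

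**3. Where the arms lie on the source study's scale.** Latest late-arm start: 12 weeks + about 60 days = 84 + 60 = 144 days after injury, against about 182 days for six months. This is an upper figure if the physician visit is no later than entry. Both arms are therefore in the source study's within-six-months category. The planned gap between arms is about 8 − 2 = 6 weeks. Starting both arms earlier does not widen that gap, so the reason given for expecting an effect at least as large does not bear on the contrast.

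**4. Does 0.432 match 22 versus 51?** If these are means, SD = (51 − 22) / 0.432 = 29 / 0.432 = 67 points. The Protocol gives no SD; for assumed SDs of 20, 30, 40 and 50, d = 29/SD = 1.45, 0.97, 0.73 and 0.58. The Protocol does not say whether 22 and 51 are means or medians, so this is a reason to check the source, not proof of an error.

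**The case against.** - **The analysis is not a two-sample t-test.** This is the strongest objection. The Protocol plans a repeated-measures mixed model with covariates, and the SAP tests a group by time interaction. Adjustment could raise power. As a rough guide from adjusting for a baseline with correlation ρ (required n shrinks by 1 − ρ²), 80% power needs ρ = √(1 − 72/86) = 0.40 at 72 per arm, √(1 − 64/86) = 0.51 at 64, and √(1 − 36/86) = 0.76 at 36 v 36. The first two are not extreme. But neither document states a correlation or a slope variance, and the SAP covariates are age, gender and initial SCAT severity. The objection stands to this extent: the figures above are benchmarks, not the power of the planned model.

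- **One-sided testing would help the pooled contrast.** It gives 83% at 72 per arm and 78% at 64. Neither document specifies it, and the Protocol's claim is made within each regimen.

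- **The transfer of the effect is openly labelled an assumption.** True, so this is not a hidden contradiction. But the Protocol goes on to defend the assumption with an argument that does not support it.

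- **A reader might infer that 0.432 is a rank correlation labelled as d.** For p=0.007, z=2.70, and z/√N = 0.432 at N of about 39; read as r it converts to d of about 0.96. But solving for N always yields some N, and d=0.432 with p=0.007 is equally consistent with about 78 per group. The source study's size is not given, so the documents cannot settle this.

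- **A reader might infer that the whole trial size rests on d=0.432.** It does not: the head-turn velocity statement is a second justification for the same 36. It fails the same check, since d=0.446 needs about 80 per group and has 46% power at 36 v 36.

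- **The SAP, dated April 2024, is written in the past tense**, so rewording changes no enrolment. That limits the benefit to honest interpretation and reporting.

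**Conclusion.** The claim of 80% power with 36 per group is wrong as written. At d=0.432 an unadjusted two-sided comparison needs about 86 per group and has 44% power at 36 v 36. The pooled Aim I contrast has 68% to 78% power at 64 to 80 per arm, short of 80% even with no dropout. This rests on a two-sided test and no gain from adjustment.

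The expectation of an effect at least as large is not supported, because both arms fall in the source study's early category. That follows from the Protocol's own timings.

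Three stronger readings go beyond the documents. That 0.432 is inconsistent with 22 versus 51 holds only if those figures are means. That it is a mislabelled r cannot be determined. That the trial is simply under- or over-sized does not follow either: a d calculated from means of 22 and 51 might be larger than 0.432, while a six-week contrast might produce a smaller effect. A null result would also remain interpretable through its estimate and confidence interval; what would mislead is reading it against the stated 80%.

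**What to change.** In Protocol section 8, or in the report if the Protocol is closed:

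1. Replace the statement of 80% power at 36 per group with power and the smallest detectable effect for AB versus CD at the actual sizes: d about 0.47 at 72 per arm and 0.50 at 64, with 0.67 for 36 v 36 within a regimen. Label these as unadjusted two-sample benchmarks. Alternatively, give the equivalent for the group-by-time mixed model, with its correlation assumptions stated.
2. Delete the expectation that the effect will be at least as large as in the source study.
3. Present d=0.432 as an untested assumption, and show power for smaller effects (43% at d=0.3 and 22% at d=0.2 with 72 per arm).
4. Check 0.432 against its source, and state whether 22 and 51 are means or medians, the SD, the number of patients and how d was obtained.

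The cost is a rewritten paragraph and a less favourable stated power. No extra patients and no change to the analysis are needed.
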